It is possible that their medical research record, including sensitive information or identifying information, may be inspected and/or copied by the study monitor and sponsor, federal or state government agencies such as the Office of Human Research Protection, or hospital accrediting agencies, in the course of carrying out their duties. If their record is inspected or copied by the study sponsor or by any of these agencies, the HNRCA will use reasonable efforts to protect their privacy and the confidentiality of their medical information.

Data are used only in aggregate and no identifying characteristics of individuals are published or presented. Results of testing are sent to participant's private physicians if participants agree to this. The participant will have a research record with the HNRCA. Every effort will be made to maintain the confidentiality of their research records for the study by the investigators

i. **How data will be coded, recorded, and stored to protect confidentiality:** Confidentiality of data is maintained by using research identification numbers that uniquely identify each individual. Safeguards are established to ensure the security and privacy of participants' study records. The information collected from participants in this study has a low potential for abuse, since the data do not address sensitive issues. Nevertheless, appropriate measures are taken to prevent unauthorized use of study information. The research ID number is used. The research records are kept in a locked room at the HNRCA. The files matching participants' names and demographic information with research ID numbers are kept in a separate room and are stored in a locked file that uses a different key from that of all other files. Only study personnel have access to these files. After the study is completed, local

data are stored with other completed research studies in a secured storage vault for a minimum of 7 years after the study has been closed out by the IRB.

iii) **Parties who will have access to the data, including the key to the identity code:** The Principal Investigator and research team will have access to study data and the identity key code.

iv) **Parties who will have access to research records:** The Principal Investigator, research team, and applicable HNRCA staff will have access to research records.

9. Alternatives: The alternative to participating in this research study is to decide not to participate. The decision to not participate will not affect the way the subject will be treated at Tufts Medical Center or Tufts University.

10. How new information will be conveyed to the study subject and how it will be documented: Any information collected during this investigation that may impact the subject's health will be communicated to the participant by the study physician. Documentation will be made in the participant's file and this information will be reported to the IRB, as necessary.

Any new information about the study that might affect subjects' willingness to continue to participate in the research study will be provided to subjects as either a letter or updated informed consent form.

11. Payment, including a prorated plan for payment: All potential subjects who attend the screening visit, whether or not they choose to participate or are ineligible will receive a screening payment of \$15. Payments will be mailed by check approximately two weeks after your visit.

Subjects that complete the baseline but not 1-month visit will be paid \$75. Subjects that complete the 1-month visit will receive an additional \$75, for a total stipend of \$150. Including the screening visit, participants can receive a total of \$165.

Table 2. Payments

Stipend	Per Visit	Number of Visits	Compensation
Screen	\$ 15.00	1	\$ 15.00
Study Visit	\$ 10.00	2	\$ 20.00
Blood Draw	\$ 10.00	2	\$ 20.00
Fecal Sample	\$ 10.00	2	\$ 20.00
DXA	\$ 20.00	2	\$ 40.00
Physical Function	\$ 25.00	2	\$ 50.00
Total			\$165

Participants will receive payment three times throughout this investigation. Participants will be paid following the screening visit, and following the baseline and 1-month study visits.

TUFTS MEDICAL CENTER/TUFTS UNIVERSITY RESEARCH PROTOCOL

Version date: 07/23/2018

ClinicalTrials.gov ID NCT02811445

Study Title: Role of the gut microbiome and the serum metabolome on lean mass and physical function in older adults

Principal Investigator: [name]

Co-Investigator: [name].
[name].

Study Doctor/Co-Investigator: [name].

Study Coordinators: [name]
[name]

I. Research Plan (Including Statistical Analysis)

40 older adults (70-85y) will be recruited from the local Boston area based on their performance on the short physical performance battery (SPPB), a measure of lower extremity physical function that includes standing balance, a 4-m walk and chair stand tests^[1]. The SPPB has been extensively validated as predictive of future disability risk and mortality in older adults^[1]. High-functioning (HF; SPPB ≥ 11) and low-functioning (LF; SPPB ≤ 8)^[2] groups will each contain 20 subjects (10 men, 10 women). Gut microbial composition is affected by age^[3, 4]. Similarly, sex and BMI are associated with gut microbiome composition^[5-7]. With the goal of minimizing gut microbial variability, I propose to recruit HF and LF subjects that are matched for age, sex and BMI but are different in terms of lean mass and physical function.

At baseline, subjects will provide a blood and stool sample that will be subjected to serum metabolomics and fecal sample 16S ribosomal RNA (16S rRNA) gene profiling, respectively. Serum metabolomics provides an analytical description of complex biological media by identifying a large number of small molecule metabolites in a given biological sample^[8]. Fecal sample 16S rRNA gene profiling will be used to identify the bacterial relative abundance that is present within each taxonomic level in each fecal sample. Lean mass and physical function will be measured in all subjects. Associations between serum metabolites, fecal bacteria, and between fecal bacteria and serum metabolites with the differentiation of HF from LF, and that are associated with lean mass and specific measures of physical function will be determined. In addition, associations between gut bacteria with circulating markers of insulin resistance and endotoxemia will be identified. Overlapping associations between gut bacteria and serum metabolites with these outcomes is expected to provide an enhanced understanding about the role of gut bacteria on mechanisms that underlie the maintenance of lean mass and physical function in older adults. The causative role of gut bacteria on the maintenance of lean mass and physical function in older adults will be examined by transplanting fecal bacteria from older adults into germ-free mice.

After 1 month, to determine the reproducibility of the baseline gut bacterial associations with lean mass and physical function, study subjects will return to provide a fecal sample that will be subjected to 16S rRNA profiling. Lean mass and physical function will be measured, and associations between fecal bacteria that collectively differentiate HF from LF, and that are associated with lean mass and specific measures of physical function will be identified and compared with baseline findings.

Statistical power: Sample size estimates are based on gut bacterial associations with the GFI^[9]. Means \pm SD for *Bacteroides/Prevotella* of 26.3 ± 13.2 and 14.8 ± 15.1 in the low-frailty and high-frailty groups, respectively, yield an effect size of 0.81, a value that is sufficient to obtain 80% power at a type-I error probability of 0.05 with a study sample size of 40 subjects. To achieve this recruitment goal, up to 150 subjects will sign the Preadmission ICF, with the goal of 40 participants completing the study.

Blood and Stool Collection: Following an overnight, 12-hour fast (beginning between 8PM-12AM the day before), eligible candidates will provide a blood sample during the initial visit (baseline) and 1-month study visits. At the screening visit, eligible subjects will be provided with a stool collection kit so that they may provide a stool sample within the 18-hour period that precedes their baseline and 1-month visits. Fasting is optional for providing the stool sample.

Measurement of insulin, glucose, lipopolysaccharide (LPS) and physical function: Serum measurement of insulin and glucose are used to calculate the homeostasis model assessment (HOMA-IR), a circulating index of insulin resistance^[10]. LPS is a component of gram-negative bacterial cell walls that can appear in the blood by microbial translocation from the gastrointestinal tract^[11], is a circulating marker of metabolic endotoxemia^[12]. LPS induces insulin resistance^[12], myotube atrophy and decreased muscle function *in vitro*^[13, 14], and decreases muscle mass in rodents^[15]. Insulin, glucose and LPS will be measured by the Nutrition Evaluation Laboratory (NEL) at the Jean Mayer HNRCA at Tufts University.

[figure not shown]
Measures of physical function including the SPPB, leg press one repetition maximum (1 RM) and 400-m will be performed by the NEPS laboratory at the Jean Mayer HNRCA at Tufts University^[16]. The importance of measuring the SPPB, the leg press 1 RM and 400-m is illustrated by the finding that reduced performance in each of these measures is associated with increased disability^[1, 17, 18] and an increased all-cause mortality risk^[1, 18, 19].

Measurement of Dietary Intake: To account for the influence of dietary intake on the gut microbiome, three 24-hour dietary recalls will be collected from enrolled study subjects. Two of these recalls will be collected on the two days prior to the baseline visit. The final dietary recall will be performed on the day of the baseline visit, for a total of three 24-hour dietary recalls.

AIM 1: Identify associations between gut bacteria and circulating metabolites that collectively differentiate HF from LF, and are associated with lean mass and physical function in older adults. [name] recently reported significant associations between circulating gut bacteria-related metabolites^[20-22] with lean and skeletal muscle mass^[23] and with measures of physical function^[16], evidence that suggests a role for gut bacteria on the maintenance of these outcomes in older adults. To date, studies aimed at identification of associations between gut bacteria and circulating metabolites with lean mass have yet to be published, whereas two studies have reported associations between gut bacteria with function^[9, 24]. However, the indices used to measure function were not specific for physical function, as questions about vision, hearing, cognition and psychosocial function were included^[25-27]. Therefore, the objective of **AIM 1** is to characterize the association between fecal bacteria and circulating metabolites that collectively differentiate HF from LF, and that are associated with lean mass and physical function in older adults.

Identification of bacterial taxa present in fecal samples: Fecal sample 16S rRNA gene profiling will be used to identify the fecal bacteria relative abundance that is present within each taxonomic level. The Phoenix Laboratory at the Tufts University Medical Center^[28] will extract fecal sample DNA, generate 16S rRNA amplicons, and assemble amplicon pools for high-throughput sequencing. The Tufts University Genomics Core Facility^[29] will then use an Illumina MiSeq System (Illumina, San Diego, CA) to target the V4 region of the 16S rRNA gene. 16S rRNA sequences will be quality filtered, clustered into Operational Taxonomic Unit (OTUs) and further analyzed using QIIME (quantitative insights into microbial ecology)^[30]. Use of 16S rRNA gene profiling allows for the determination of bacterial taxa other than *E. coli* and *Enterobacteriaceae* that may be different in HF when compared with LF older adults. For example, various bacterial species other than *E. coli* are capable of BCAA synthesis^[31]. Furthermore, the BCAA catabolic metabolites 2-oxoisovalerate and 4-methyl-2-oxopentanoate are negatively associated with colonic *Lactobacillus spp.* abundance^[21].

Bacterial taxa that differentiate HF from LF older adults: Principal co-ordinate analysis (PCoA) of the phylogeny based Unifrac distance metric^[32], which are derived from OTUs^[33] will be used to determine if the overall gut microbial profile in HF is significantly different when compared with LF older adults. The analysis of similarities function in the statistical software package PRIMER 6 (PRIMER-E Ltd., Lutton, UK^[34]) will be used to determine between-group statistical significance ($p \leq 0.05$). To identify bacterial taxa and relative abundance that are significantly different in HF when compared with LF older adults, linear discriminant analysis effect size (LEFSE)^[35] will be used. LEFSE is an algorithm for high-dimensional biomarker discovery and explanation that identifies bacterial taxa that characterize the difference between two or more biological conditions.

Test the causative role of human gut bacteria on the maintenance of lean mass and physical function: Although identification of gut bacteria that are associated with lean mass and physical function is an important observation, transplanting intact uncultured human fecal microbiota into recipient germ-free mice permits the donors' communities to be replicated and the causative role of their microbiota on outcome measures to be

discerned. For example, transplantation of human gut microbiota from 4 female twins discordant for kwashiorkor (the condition caused by severe dietary protein deficiency) into germ-free mice resulted in 86-90% of species-level taxa and ~90% of the functions encoded by the donor's microbiome being found in recipient mice, thereby implicating the gut microbiota as a causal factor on kwashiorkor^[36].

Transplantation of gut microbiota from a healthy human adult into germ-free mice resulted in all bacterial phyla, 92% of bacterial classes and 88% of genus-level taxa being detected in the feces of recipient germ-free mice^[37]. Human gut bacteria-containing mice fed a high-fat western diet gained significantly more adiposity during the two weeks following transplantation than mice that consumed a low-fat, plant polysaccharide-rich diet^[37], evidence that demonstrates a causative role for diet-induced increases in adiposity by human gut bacteria. Similarly, transplantation of human gut microbiota from 3 twins (2 female and 1 male) discordant for obesity into germ-free mice resulted in ~75% of family-level bacterial taxa and 99.7% of the functions encoded by the donor's microbiome being represented in recipient mice, thereby resulting in a greater increase in adiposity in mice colonized with fecal microbiota from obese, when compared with its lean co-twin^[38].

Collectively, these studies demonstrate that transfer of gut bacteria from humans into germ-free mice is highly efficient, functions encoded by the transferred microbiome are maintained, and phenotypes are transmissible. The objective of **AIM 2** is to test the causative role of human gut bacteria on the maintenance of lean mass and physical function by transferring fecal microbiota from HF and LF older adults into germ-free mice.

Statistical Power: Germ-free mice colonized with fecal bacteria from obese humans gained significantly more adiposity than germ-free mice colonized with fecal bacteria from their lean co-twin ($10.0\% \pm 5.0\%$ compared with $0.1\% \pm 2.0\%$), a result that was significant 15 days after colonization^[38]. Based on these data, the resulting effect size of 2.6 is sufficient to obtain 99% power at a type-I error probability of 0.05 with a sample size of 12 human subjects. Accordingly, with the goal of identifying a similar change in lean mass and physical function, I propose to transfer fecal bacteria from 12 older adults into germ-free mice.

III.2.a Colonization of germ-free mice with human gut bacteria from HF and LF older adults: Fecal samples from 6 HF (3 males, 3 females) and 6 LF (3 males, 3 females) older adults will be transferred into sex-matched (with the goal of minimizing sex-associated gut microbial variability^[6, 7]) C57BL/6J germ-free mice for a duration of 5 weeks at the Germ-Free and Gnotobiotic Microbiology Core at the Harvard Digestive Disease Center (HDDC; Boston, MA). The transmissible effect of host phenotype by gut microbiota has been previously reported by transferring human fecal bacteria into C57BL/6J germ-free mice^[36-38]. Furthermore, the homogenous genetic background provided by inbred C57BL/6J germ-free mice allows for a cleaner system to dissect signals from gut bacteria-host interactions, and improves experimental reproducibility, when compared with genetically heterogeneous GFM^[39]. One fecal sample from each human donor will be transferred into 5 separate germ-free mice (based on the range of germ-free mice used in human fecal transfer experiments^[36, 38]), resulting in 60 mice colonized with human gut microbiota. 5 germ-free mice will not be colonized with fecal bacteria from older adults (germ-free control group). All recipient mice will be fed *ad libitum* with a commercial, sterilized mouse chow^[38]. Food consumption will be measured daily to ensure that changes in lean mass or physical function do not result because of differences in food intake.

III.2.b Measurement and analysis of the change in lean mass and physical function in mice colonized with human gut bacteria: Lean mass and physical function in mice colonized with human gut bacteria will be measured on day 0 (prior to colonization), 9, 18, 27 and 35 days post-colonization at the HDDC. Lean mass will be measured with use of quantitative magnetic resonance imaging (EchoMRI-3in1 instrument, Houston, TX)^[38]. Muscle strength will be measured using a grip strength meter for mice (Technical and Scientific Equipment GmbH, Bad Homburg, Germany)^[40]. Each mouse will firmly grab the pulling bar of the grip strength meter with both forepaws and then pulled gently backwards until it releases its grip. The peak force of each trial is considered the grip strength. A 1-liter beaker filled with water will be used as a swimming pool to test endurance capacity^[41].

A weight (10% of body weight) will be attached to the tail of a mouse, which is then placed in the water. The amount of time that the mouse is able to maintain complete buoyancy will be recorded. The EchoMRI, grip strength meter and beaker/weight will be sterilized prior to use to ensure that germ-free conditions at the HDDC are maintained. Because [name] has previously measured lean mass and physical function in mice^[42, 43], he will perform these measurements at the HDDC.

Differences for the change in lean mass and physical function will be calculated relative to initial values. Statistical significance for the change in lean mass and physical function will be compared in mice colonized with fecal bacteria from HF or LF human donors and for germ-free mice that were not colonized with human gut bacteria with use of two-way ANOVA^[38].

III.2.c Bacterial taxa identification and association with the change in lean mass and physical function in mice colonized with human gut bacteria: Fecal pellets will be obtained from 5 germ-free mice at baseline, which will not be colonized with human gut bacteria. Five weeks post-colonization with human gut bacteria, fecal pellets will be collected from 60 mice (30 each from the HF and LF donors) and from the 5 germ-free mice that did not receive human gut bacteria. 16S rRNA gene profiling on these 70 fecal pellets will be performed as described in **Section III.1.a**.

Associations between gut bacteria-containing principal components and individual bacterial taxa with the 35-day change in lean mass, mouse grip strength and endurance capacity will be identified as described in **Section III.1.b**. Supervised machine learning (random forest) will be used to predict whether a sample came from a mouse colonized with HF or LF donor microbiota^[44].

The gut bacterial profile that is associated with the change in lean mass and physical function in mice colonized with HF or LF human fecal bacteria is expected to be similar to the gut bacterial profile that is associated with differentiation of HF from LF older adults. CIA will be used to identify associations between circulating metabolites with gut bacteria that collectively differentiate mice colonized with HF or LF gut bacteria.

REFERENCES

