TUFTS MEDICAL CENTER/TUFTS UNIVERSITY RESEARCH PROTOCOL

Version date: 07/23/2018

ClinicalTrials.gov ID NCT02811445

Study Title: Role of the gut microbiome and the serum metabolome on lean mass and physical function in older adults

Principal Investigator: [name]

Co-Investigator: [name].
[name].

Study Doctor/Co-Investigator: [name].

Study Coordinators: [name]
[name]

I. Research Plan

40 older adults (70-85y) will be recruited from the local Boston area based on their performance on the short physical performance battery (SPPB), a measure of lower extremity physical function that includes standing balance, a 4-m walk and chair stand tests^[1]. The SPPB has been extensively validated as predictive of future disability risk and mortality in older adults^[1]. High-functioning (HF; SPPB ≥ 11) and low-functioning (LF; SPPB ≤ 8)^[2] groups will each contain 20 subjects (10 men, 10 women). Gut microbial composition is affected by age^[3, 4]. Similarly, sex and BMI are associated with gut microbiome composition^[5-7]. With the goal of minimizing gut microbial variability, I propose to recruit HF and LF subjects that are matched for age, sex and BMI but are different in terms of lean mass and physical function.

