Bacterial taxa that differentiate HF from LF older adults: Principal co-ordinate analysis (PCoA) of the phylogeny based Unifrac distance metric^[32], which are derived from OTUs^[33] will be used to determine if the overall gut microbial profile in HF is significantly different when compared with LF older adults. The analysis of similarities function in the statistical software package PRIMER 6 (PRIMER-E Ltd., Lutton, UK^[34]) will be used to determine between-group statistical significance ($p \leq 0.05$). To identify bacterial taxa and relative abundance that are significantly different in HF when compared with LF older adults, linear discriminant analysis effect size (LEFSE)^[35] will be used. LEFSE is an algorithm for high-dimensional biomarker discovery and explanation that identifies bacterial taxa that characterize the difference between two or more biological conditions.

Test the causative role of human gut bacteria on the maintenance of lean mass and physical function: Although identification of gut bacteria that are associated with lean mass and physical function is an important observation, transplanting intact uncultured human fecal microbiota into recipient germ-free mice permits the donors' communities to be replicated and the causative role of their microbiota on outcome measures to be

discerned. For example, transplantation of human gut microbiota from 4 female twins discordant for kwashiorkor (the condition caused by severe dietary protein deficiency) into germ-free mice resulted in 86-90% of species-level taxa and ~90% of the functions encoded by the donor's microbiome being found in recipient mice, thereby implicating the gut microbiota as a causal factor on kwashiorkor^[36].

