A weight (10% of body weight) will be attached to the tail of a mouse, which is then placed in the water. The amount of time that the mouse is able to maintain complete buoyancy will be recorded. The EchoMRI, grip strength meter and beaker/weight will be sterilized prior to use to ensure that germ-free conditions at the HDDC are maintained. Because [name] has previously measured lean mass and physical function in mice^[42, 43], he will perform these measurements at the HDDC.

Differences for the change in lean mass and physical function will be calculated relative to initial values. Statistical significance for the change in lean mass and physical function will be compared in mice colonized with fecal bacteria from HF or LF human donors and for germ-free mice that were not colonized with human gut bacteria with use of two-way ANOVA^[38].

III.2.c Bacterial taxa identification and association with the change in lean mass and physical function in mice colonized with human gut bacteria: Fecal pellets will be obtained from 5 germ-free mice at baseline, which will not be colonized with human gut bacteria. Five weeks post-colonization with human gut bacteria, fecal pellets will be collected from 60 mice (30 each from the HF and LF donors) and from the 5 germ-free mice that did not receive human gut bacteria. 16S rRNA gene profiling on these 70 fecal pellets will be performed as described in **Section III.1.a**.

Associations between gut bacteria-containing principal components and individual bacterial taxa with the 35-day change in lean mass, mouse grip strength and endurance capacity will be identified as described in **Section III.1.b**. Supervised machine learning (random forest) will be used to predict whether a sample came from a mouse colonized with HF or LF donor microbiota^[44].

The gut bacterial profile that is associated with the change in lean mass and physical function in mice colonized with HF or LF human fecal bacteria is expected to be similar to the gut bacterial profile that is associated with differentiation of HF from LF older adults. CIA will be used to identify associations between circulating metabolites with gut bacteria that collectively differentiate mice colonized with HF or LF gut bacteria.

A. Subject Characteristics

1) Subject eligibility criteria:

a) Inclusion criteria:

- i) Willing and able to sign the IRB approved informed consent form
- ii) Male and Female: males, 70-85y; females, 70-80y

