- iii) BMI: males < 35, females <30 kg/m²
- iv) Willing to come to the HNRCA laboratory for baseline and 1-month follow-up study visits
- v) SPPB ≥ 11 (“High-Functioning”, HF; 20 subjects: 10 males, 10 females)
- vi) 4 ≤ SPPB ≤ 8 (“Low-Functioning”, LF; 20 subjects: 10 males, 10 females)

b) Exclusion Criteria:

- i) Non-English speaker
- ii) Acute or terminal illness
- iii) Surgery in the past 6 months
- iv) Lower extremity fracture within the past 6 months
- v) Myocardial infarction in the past 6 months
- vi) Coronary artery disease, peripheral vascular disease, previous stroke, or history of transient ischemic attacks
- vii) Cognitive impairment (MMSE score < 23)
- viii) Uncontrolled hypertension (> 160/100 mmHg)
- ix) Neuromuscular disease or drugs affecting neuromuscular function
- x) Androgen therapy in males
- xi) Estrogen therapy in females

- xii) Significant immune disorder
- xiii) Kidney Failure
- xiv) Pancreatic disease
- xv) Diabetes
- xvi) Gastrointestinal or malabsorption diseases
- xvii) History of cholecystectomy
- xviii) Use of probiotics, prebiotics or antibiotics in the past 3 months
- xix) The subject has any other condition, which in the opinion of the Investigator, precludes the subject's participation in the trial.
- xx) With the goal of matching the HF and LF groups for age, sex, and BMI, subjects may be excluded because their age, sex or BMI puts them outside the range needed for this study.

c) **Withdrawal/Termination criteria:** Subjects may stop participating in this study at any time for any reason. If an enrolled subject decides to withdraw from this research study, they will be asked to inform the Principal Investigator ([name]), the Lab Director ([name]), or his representative. The principal investigator may stop participation in this research study without the subject's permission for any of the following reasons:

- The participant did not adhere to any or all HNRCA volunteer rules and regulations
- Participant does not follow the study procedures
- There has been a change in the subject's health that would make the subject ineligible

B. Risk/benefit assessment:

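### HF and LF are matched on age, sex and BMI only by discretionary exclusion, and the HF/LF tests adjust for none of them, so leftover age or BMI imbalance goes uncorrected

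*SAP*

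**What the plan says.** Both documents, in the opening paragraph of section I, give the reason for matching. The Protocol says "Gut microbial composition is affected by age", and the SAP adds that "sex and BMI are associated with gut microbiome composition". The conclusion is "I propose to recruit HF and LF subjects that are matched for age, sex and BMI", and the stated purpose is "With the goal of minimizing gut microbial variability".

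Sex is fixed by quota at 10 men and 10 women per group. Age and BMI have no quota. The only mechanism for them is Protocol A.1.b, exclusion criterion (xx): "subjects may be excluded because their age, sex or BMI puts them outside the range needed for this study". I found no caliper, pairing rule, tolerance or balance check. The eligibility windows in Protocol A.1.a are "males, 70-85y; females, 70-80y" for age, and below 35 (men) or below 30 (women) kg/m² for BMI.

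The HF/LF tests are in the paragraph on bacterial taxa that differentiate HF from LF, with the same text in both documents. For the overall profile, the SAP names "The analysis of similarities function in the statistical software package PRIMER 6", applied to UniFrac distances. The Protocol says this function "will be used to determine between-group statistical significance", at p ≤ 0.05. Individual taxa are tested with LEFSE. HF/LF is the only factor named, and no covariate, stratum, pair term or adjusted sensitivity analysis is described.

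**The concern.** The plan identifies age and BMI as influences on the microbiome before any data are seen, and then leaves them out of the comparison. Two consequences follow.

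- **Imbalance.** If the LF group ends up somewhat older or heavier, a difference due to age or BMI can be reported as a microbial signature of physical function.
- **Precision.** Whatever share of the outcome variance age and BMI explain remains in the error, in a comparison of only 20 against 20.

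ANOSIM works on ranked distances between labelled groups and cannot take a continuous covariate. Adjusting the test of overall profile therefore needs a different named test, not just an extra sentence. Age is known from eligibility, and height and weight are measured at screening, baseline and 1 month (Protocol C.1.iii), so no new data are needed.

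**Working it through.** The calculations use a two-sample t-test (unadjusted) and ANCOVA (adjusted) on one continuous outcome, as a proxy for ANOSIM and LEFSE.

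**1. The plan's own figure.** Inputs from the Statistical power paragraph: means 26.3 and 14.8, SDs 13.2 and 15.1, total N = 40, alpha 0.05 with sidedness not stated.

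- Pooled SD = √[(13.2² + 15.1²)/2] = 14.18. d = 11.5/14.18 = 0.81, as stated.
- Noncentrality at 20 per group = 0.81 × √(20/2) = 2.56, with 38 df.
- Power = 80.8% one-sided and 70.4% two-sided. The stated 80% reproduces only one-sided, so both are shown below.

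**2. Power with age and BMI in the model.** R2 is the share of within-group outcome variance that they jointly explain. The documents do not give it, so the range is assumed. Adjusted effect = 0.81/√(1 − R2), with 40 − 2 − 2 = 36 df.

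| R2 | Adjusted effect | Two-sided power | One-sided power |
|---|---|---|---|
| Unadjusted | 0.810 | 70.4% | 80.8% |
| 0 | 0.810 | 70.3% | 80.7% |
| 0.04 | 0.827 | 72.0% | 82.1% |
| 0.09 | 0.849 | 74.3% | 83.9% |
| 0.16 | 0.884 | 77.6% | 86.4% |
| 0.25 | 0.935 | 82.1% | 89.6% |

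Adding sex (35 df) with R2 = 0 gives 70.2% two-sided, a cost of 0.2 point. The formula assumes the covariates are close to balanced. A 0.5 SD gap in one covariate inflates the variance of the adjusted difference by 1 + 0.5²/4 = 1.06.

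**3. False positives from leftover imbalance.** Assume no true HF/LF effect, a group gap g (in SDs of the covariate), and correlation rho between covariate and outcome. The unadjusted mean difference is shifted by rho × g SD, so the noncentrality is rho × g × √10 with 38 df. Two-sided rejection rates:

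| Gap | rho 0.2 | rho 0.3 | rho 0.4 | rho 0.5 |
|---|---|---|---|---|
| 0.25 SD | 5.3% | 5.6% | 6.1% | 6.7% |
| 0.5 SD | 6.1% | 7.5% | 9.5% | 12.0% |

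Simulation (20,000 runs per cell) agrees with these rates and puts the adjusted test at about 5% throughout. The spurious shift runs from 0.2 × 0.25 = 0.05 SD to 0.5 × 0.5 = 0.25 SD, which is 6% to 31% of the design effect of 0.81.

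For scale, if men's ages were uniform over 70-85, the SD would be 15/√12 = 4.3 years. Gaps of 0.25 and 0.5 SD would then be about 1.1 and 2.2 years.

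**4. Does matching make the unadjusted test conservative?** Only if it is close to pairwise.

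- With each LF value set to an HF partner's value plus 0.2 SD noise, simulated type-I error is about 4%, 3.4% and 2.5% at rho 0.3, 0.4 and 0.5.
- With independent sampling and no gap, it is 5% at every rho.

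**The case against.** The fair defence is that matching in the design followed by an unadjusted comparison is a legitimate choice, especially in what Protocol section D.3 calls a pilot. Up to 150 people may sign the preadmission consent to yield 40 completers, which leaves room to match well under criterion (xx). At a 0.25 SD gap the false-positive rate barely moves, and at R2 = 0.04 adjustment gains only 1.6 points two-sided (1.3 one-sided). All of this stands, and it limits the size of the point. It does not remove the point: nothing obliges the matching to be tight, and adjustment costs almost nothing if age and BMI prove irrelevant.

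Three stronger readings are tempting, and the documents do not support them.

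- **That the planned test is conservative because the groups are matched.** This needs near-exact pairs, and the plan promises only a range. Even under close pairing, simulated unadjusted power is about 71-73% for rho 0.3 to 0.5, slightly above the 70.4% without matching. The loss is relative to a better analysis.
- **That ANOSIM gives up a very large amount of power by ignoring age and BMI.** A distance-based simulation with strong assumed effects (1 SD per SD of age on one of five axes and of BMI on another) gave 59% for ANOSIM, 70% for unadjusted PERMANOVA and 91% for adjusted PERMANOVA. About 11 of those 32 points come from changing the test, and no figure in the documents supports slopes of that size.
- **That the groups will be badly imbalanced.** The documents do not predict any imbalance. They only fail to prevent or correct it.

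Both documents cite a Section III.1.b that does not appear in the text. It is cited for associations with change in lean mass and function in mice. The HF/LF test in older adults is described separately and without adjustment, so that section would not repair it.

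**Conclusion.** The point holds in a conditional form. The plan names age and BMI as influences on the microbiome, matches on them loosely, and leaves them out of both HF/LF tests. Residual imbalance is therefore uncorrected, and explained variance stays in the error.

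For R2 of 0.04 to 0.25, adjustment is worth about 1.6 to 11.7 points of power two-sided (70.4% to 72.0-82.1%) or 1.3 to 8.8 points one-sided (80.8% to 82.1-89.6%). For rho of 0.2 to 0.5, the unadjusted false-positive rate is about 5-7% at a 0.25 SD gap and about 6-12% at 0.5 SD. R2, rho and the gap are all assumptions, and the t-test stands in for the distance-based and taxon-level tests. The unadjusted comparison is not invalid in itself, but a cheap, better-protected analysis of the same data is available and should be specified in advance.

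**What to change.** In the paragraph on taxa that differentiate HF from LF, in both documents:

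- **Overall profile.** Test HF against LF by PERMANOVA on the same UniFrac distances. Enter baseline age, BMI (both continuous) and sex before HF/LF, and permute residuals under the reduced model. Include sex because it is a design factor and because the age and BMI limits differ by sex. Keep ANOSIM as a descriptive or sensitivity result.
- **Individual taxa.** Keep LEFSE for discovery. Add a linear model of HF/LF for the taxa, adjusted for age, BMI and sex, as a check that flagged taxa are not explained by age or BMI. State the abundance transformation, the handling of zeros and the false-discovery-rate control before analysis.
- **Balance.** Report achieved age and BMI by group.

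The cost is three degrees of freedom (about 0.2 point of two-sided power in the proxy if none of the three matters), a change of named test and a little more analysis work. No extra participants, visits or measurements are needed.
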